5.3.3 Analysis Method

The data will be analyzed according to the randomized treatment.

For the key secondary endpoints, the CMH analysis for difference in proportions, adjusted for the stratification factors (age [<65 and ≥ 65 years] and use of IMV [yes/no]) will be performed. The comparison between treatment groups will be based on CI-estimates and p-values obtained from this analysis.

A positive value on the common proportion (risk) difference using the Mantel-Haenszel method indicates that the proportion of participants with ‘Sustained clinical improvement at day 28’/‘death by day 28’ is larger in the experimental treatment group. The actual values of the stratification factors will be used, not as randomized.

As a sensitivity analysis, a logistic regression model will be estimated that is adjusted for the treatment group, but also adjusted for additional baseline covariates. The covariates are the following: CRS at baseline (≤ 3 vs > 3), Remdesivir at baseline (yes/no), Glucocorticoids at baseline (yes/no), Number of Comorbidities (0/1/2/ ≥ 3), Sex (Male/Female), Race (Asian/Black or African American/White/Unknown or Not reported), Ethnicity (Hispanic or Latino/Not Hispanic or Latino), Free IL-6 at screening, CRP at screening, ferritin at screening, LDH at screening (high/low/normal) and albumin (low/not low) at screening. Each of the additional baseline covariates will be added to the model to estimate the individual effect of these covariates, after which a stepwise selection method will be applied. A covariate will be added to the model if it is significant at the 25% significance level, while the covariate in the model has to be significant at the 0.15% level for it to remain in the model. In the final logistic regression model the treatment difference in proportions will be estimated. This will be done as follows: in each treatment group the proportion of participants with improvement will be estimated using the average value observed the study (across treatment groups) for both the continues and categorical covariates (based on 0/1 coding for categorical). The delta method will be used for the confidence interval.

Comorbidities considered: Obesity (BMI ≥ 30), Diabetes, Serious Heart Condition/Coronary Heart Disease, Chronic Obstructive Lung Disease, Chronic Kidney Disease and Cancer.

Analyses of qualitative comparison between pre-interim analysis and post-interim analysis for treatment effect on the key secondary endpoints in the population with confirmed critical COVID-19 disease will be conducted to check the consistency in the study.

The key secondary analyses will be repeated for the ITT population, including the participants with severe confirmed COVID-19 disease.

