2.2.3 Primary Analysis Set

The Primary analysis set consists of all participants in the ITT analysis set with confirmed critical COVID-19 disease defined as score of 4 or 5 on the CRS scale at baseline. For more details on CRS score please refer to Section 5: Efficacy. Treatment groups as randomized will be used for the analysis using this analysis set (Primary analysis set as Randomized).

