2.6 Definition of Subgroups

Subgroups used for analyses of different endpoints are defined in the Table 2 below.

Descriptive statistics will be produced for the different subgroups.

Table 2: Subgroup definition

| Subgroup | Definition | Endpoints |
|------------------------------------|--|--|
| Age group (years) | 
 • <65 years • ≥ 65 years | 
 - Participants' demographics information, baseline disease characteristics, and disposition information - Selected Efficacy - Safety (selected laboratory test results and AE tables) |
| CRS score at baseline ¹ | 
 CRS ≤ 3 CRS ≤ 4 CRS=4 CRS=5 | 
 - Participants' demographics information, baseline disease characteristics, and disposition information - Selected Efficacy - Safety (selected laboratory test results and Adverse events results) |
| | | ○ |

| Subgroup | Definition | Endpoints |
|------------------------|--|--|
| Center ² | 
 Highest recruiter center (located over 2 sites) All other centers | Efficacy (primary and key secondary endpoints) |
| Interim Analysis | 
 Included in Interim Analysis Not included in Interim Analysis | Efficacy (primary and key secondary endpoints) |
| Free IL-6 at screening | 
 $\leq 33\%$ percentile > 33 and $\leq 66\%$ percentile $> 66\%$ percentile | Efficacy (primary and key secondary endpoints) |
| CRP at screening | 
 $\leq 33\%$ percentile > 33 and $\leq 66\%$ percentile $> 66\%$ percentile | Efficacy (primary and key secondary endpoints) |

¹ CRS=5 corresponds to “Use of IMV at the time of randomization”. For descriptive statistics, CRS score at baseline with the subgroups as defined will be used. For inferential statistics, the models should include a baseline CRS flag (≤ 3 /> 3) in combination with the stratification factor. Baseline CRS will not be included in the model.

² Highest recruiter center (located over 2 sites: US1006 & US10033)

Additional subgroup analysis may be specified in a separate analysis plan and reported separately from the clinical study report. These may include subgroups according to baseline C-Reactive Protein or baseline Albumin values.

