As a sensitivity analysis, a Cox proportional hazards model will be estimated that is stratified for the stratification factors, but also adjusted for additional baseline covariates on top of treatment. The covariates are the following: CRS at baseline (≤ 3 vs > 3), Remdesivir at baseline (yes/no), Glucocorticoids at baseline (yes/no), Number of Comorbidities (0/1/2/ ≥ 3), Sex (Male/Female), Race (Asian/Black or African American/White/Unknown or Not reported), Ethnicity (Hispanic or Latino/Not Hispanic or Latino), Free IL-6 at screening, CRP at screening, ferritin at screening, LDH at screening (high/low/normal) and albumin (low/not low) at screening. Each of the additional baseline covariates will be added to the model to estimate the individual effect of these covariates, after which a stepwise selection method will be applied. A covariate will be added to the model if it is significant at the 25% significance level, while the covariate in the model has to be significant at the 0.15% level for it to remain in the model. The hazard ratio will be estimated in the final Cox proportional hazard model.

Comorbidities considered: Obesity (BMI ≥ 30), Diabetes, Serious Heart Condition/Coronary Heart Disease, Chronic Obstructive Lung Disease, Chronic Kidney Disease and cancer. Time to sustained clinical improvement can be considered as a composite of two endpoints: time to improvement in the survivors as well as death by day 28. These two components will therefore also be analyzed separately. That is, the analyses described in the previous paragraph will be repeated in the subgroup of participants that do not die by day 28 and the analyses for the endpoint of death by day 28 are described in section [5.3](#).

At this moment it is difficult to predict whether prohibited medication will be used, in what frequency in the two treatment arms and what their efficacy might be. Therefore, the impact of prohibited medication will be explored retrospectively.

Analyses of qualitative comparison between pre-interim analysis and post-interim analysis for treatment effect on the primary endpoint in the population with confirmed critical COVID-19 disease will be conducted to check the consistency in the study.

The primary analysis will be repeated for the ITT population, including the participants with severe confirmed COVID-19 disease.

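### The logistic sensitivity model for the key secondary endpoints (SAP 5.3.3, reused in 5.4.2) omits age group and IMV, the two stratification factors, and its CRS flag is constant in the Primary set

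*SAP*

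**What the plan says.** SAP 5.3.3 makes the CMH comparison of proportions the main analysis of both key secondary endpoints, "adjusted for the stratification factors (age [<65 and ≥ 65 years] and use of IMV [yes/no]) will be performed". It then adds a sensitivity analysis in which "a logistic regression model will be estimated that is adjusted for the treatment group, but also adjusted for additional baseline covariates".

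The list has 12 candidates: the CRS flag (≤3 vs >3), remdesivir, glucocorticoids, comorbidity count, sex, race and ethnicity, followed by "Free IL-6 at screening, CRP at screening, ferritin at screening, LDH at screening (high/low/normal) and albumin (low/not low) at screening". Selection is stepwise: "A covariate will be added to the model if it is significant at the 25% significance level", and a covariate must reach the 0.15% level to stay. The final model yields a difference in proportions, predicted at average covariate values, with a delta-method interval.

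Four other places bear on the point.
- SAP 5.2.3: the Cox sensitivity model for the primary endpoint uses the same list but is "stratified for the stratification factors, but also adjusted for additional baseline covariates on top of treatment".
- SAP 2.2.3: the Primary set is restricted to "confirmed critical COVID-19 disease defined as score of 4 or 5 on the CRS scale at baseline".
- SAP 2.6, Table 2, footnote 1: "For inferential statistics, the models should include a baseline CRS flag" (≤3 / >3), to be combined with the stratification factor. The same footnote equates CRS 5 with IMV use at randomization.
- SAP 5.4.2: the proportional odds model names treatment, the CRS flag and the stratification factors. The incidence endpoints are analysed with the logistic regression of 5.3.

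**The concern.** A sensitivity analysis of this kind should keep the main analysis's adjustment and add to it. Here the two factors chosen for stratified randomization are in the main analysis and missing from the check. The respiratory-status term that remains cannot stand in for them in the Primary set. The split that does vary there is CRS 4 vs 5, which footnote 1 equates with IMV, and IMV is one of the omitted factors.

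What is at stake is a coherent robustness check for Day 28 improvement and mortality and, through 5.4.2, the stated analysis of the incidence endpoints, which has no CMH analysis in front of it in the SAP.

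**Working it through.** **1. The plan's own figure.** SAP 1.4 gives 74 + 37 participants, 1-sided 5%, and at least 80% power for both key secondary endpoints. Take power = Φ[(|p1−p0| − 1.645·SE0)/SE1], where SE0 uses the pooled rate and SE1 the separate rates.
- Improvement, 30% vs 55%: pooled rate 0.467, SE0 = 0.1004, SE1 = 0.0950, so power = Φ(0.893) = 81.4%.
- Mortality, 40% vs 15%: pooled rate 0.233, SE0 = 0.0852, SE1 = 0.0906, so power = Φ(1.213) = 88.7%.

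Both agree with the plan.

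**2. The models side by side.**

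| Analysis | Age group and IMV | CRS ≤3 / >3 |
|---|---|---|
| CMH, 5.3.3 | yes | no |
| Cox sensitivity, 5.2.3 | yes, as strata | candidate |
| Proportional odds, 5.4.2 | yes | yes |
| Logistic, 5.3.3 (reused in 5.4.2) | not named | candidate |

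**3. The CRS flag in the Primary set.** With CRS 4 or 5 only, every participant has CRS >3. A design matrix with intercept, treatment and the flag has 3 columns and rank 2, so the flag duplicates the intercept and adjusts for nothing.

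**4. The stay level.** Take a balanced binary covariate, n = 111 and an event rate near 50%. The standard error of its log odds ratio is about 1/√(111 × 0.25 × 0.25) = 0.380. At OR 3 the expected z is 1.099/0.380 = 2.89, and the two-sided 0.15% cutoff is 3.17, so the chance of retention is about 39%. At OR 2 it is 9% and at OR 4 it is 68%. At a 15% level the three figures would be 65% (OR 2), 93% (OR 3) and 99% (OR 4). With moderate covariate effects the final model may contain treatment only.

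**5. Power and type I error.** The documents give no prevalences or prognostic effects, so these are assumptions. Simulation used 3,000 trials per setting, N = 111, 2:1 stratified permuted blocks and 1-sided 5% Wald tests, with no covariates other than treatment and the two factors.

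| Setting | Without factors | With factors |
|---|---|---|
| 40% aged ≥65, 40% IMV, OR 3 each: improvement 30% vs 55% | about 83% | about 86% |
| Same: mortality 40% vs 15% | 90% | 92% |
| OR 2 each: mortality 40% vs 15% | 89% | 90% |
| Type I error, OR 3 each | 4.0% | 5.1% |

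With 30% on IMV instead, improvement power without and with the factors is 81.3% and 83.1% at OR 2, and 83.6% and 89.4% at OR 6. Type I error is 5.4% and 6.2% at OR 2, and 2.9% and 5.0% at OR 6 (Monte Carlo standard error about 0.4 points).

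**6. The quantity reported.** The SAP estimates expit(b0 + b1 + b′x̄) − expit(b0 + b′x̄), a difference at the average covariate vector x̄. Marginal standardisation averages expit(b0 + b1 + b′xᵢ) − expit(b0 + b′xᵢ) over participants i. For improvement (true difference 0.250, prevalences 40%, OR 3 each) the mean estimates are:
- Mantel-Haenszel: 0.252
- logistic without the factors: 0.251
- logistic with the factors, at average covariates: 0.283
- logistic with the factors, standardised: 0.251

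For mortality (true difference −0.250) a separate run gives −0.250 for Mantel-Haenszel, −0.251 without the factors, and −0.265 with them at average covariates.

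**The case against.** The strongest reply is that little depends on this model. SAP 5.3.3 bases the treatment comparison on the CMH, which has both factors, and the logistic model carries no alpha or power requirement. That stands, and it limits the weight of the point.

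A second reply is that SAP 5.1.2, which calls for actual values of the stratification factors in all analyses, together with Table 2 footnote 1, already brings the factors in. This stands only in part. Sections 5.2.3, 5.3.3 and 5.4.2 use the phrase about actual values to separate actual from as-randomized strata, so 5.1.2 is best read that way. Footnote 1 does point to including them, which makes 5.3.3 inconsistent with it. A programmer following 5.3.3 would leave them out.

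Third, the CRS flag has a purpose: it varies in the ITT repeat. That is correct, and the flag should stay there.

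Several stronger readings are tempting and not supported.
- A reader might infer that the logistic model adjusts for less than the CMH. As specified it adjusts for different things, since 11 candidates other than the flag remain. Only after selection might it shrink to treatment alone.
- A reader might take the flag for the only severity covariate. Inflammatory and laboratory markers, glucocorticoid use and comorbidities are also listed.
- A reader might expect an attenuated treatment effect. That concerns the odds ratio; the SAP reports a difference in proportions, which the omission barely moves.
- A reader might size the mortality loss at 40% vs 20%. That is the assumption for the primary endpoint; SAP 1.4 targets 40% vs 15% for the key secondary.

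**Conclusion.** The inconsistency is real and should be corrected. The logistic model in SAP 5.3.3 does not include age group or IMV, contrary to the CMH in the same section, the Cox model in 5.2.3, the proportional odds model in 5.4.2 and Table 2 footnote 1. Its respiratory-status flag adjusts for nothing in the Primary set.

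The size is modest: about 3 points of Wald power for improvement and 2 for mortality at OR 3 and 40% prevalence for each factor, both assumed. Without the factors the test is near nominal at OR 2 and conservative at OR 3 or more, so there is no sign that the omission inflates type I error. The point matters most in 5.4.2, where this model is the stated analysis. The correction also has to cover the estimator. Adding the factors while predicting at average covariates would shift the improvement estimate from about 0.25 to 0.28 for reasons unrelated to robustness.

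**What to change.** In SAP 5.3.3, and by reference in 5.4.2:
- Force treatment, age group (<65 / ≥65) and IMV (yes/no), at actual values, into every logistic model, exempt from stepwise selection.
- Use the CRS ≤3 / >3 flag only in the ITT set. In the Primary set, CRS 4 vs 5 largely duplicates IMV and need not be added.
- Estimate the difference in proportions by marginal standardisation with a delta-method interval, so that it targets the same risk difference as the CMH.
- Confirm that the 0.15% stay level is intended.

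The cost is SAP wording, two model terms and a change to one estimation step. No new data are needed.

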5.3.2 Key Secondary Estimands

Clinical improvement at Day 28

Population: The population of interest are hospitalized patients between ≥ 18 and <85 years old with confirmed critical COVID-19 disease.

Endpoint: Sustained clinical improvement at Day 28 (yes/no)

Interventions: Received Sirukumab 5 mg/kg (IV single dose infusion on Day 1) and placebo (IV infusion on Day 1), both on top of SOC.

Intercurrent Events:

- Death as intercurrent event is handled in a composite strategy as it is the worst category on the clinical scale. Participants that died at Day 28 or earlier will be considered as failure (Sustained clinical improvement at Day 28=no), irrespective of whether a clinical improvement occurred prior to death.
- The intercurrent event of the use of prohibited medication is handled in a treatment policy strategy: data will be used as observed.
- The intercurrent event of discharge to the alternate care settings ‘different hospital’, ‘acute care facility’, ‘subacute care facility’ or ‘hospice/palliative discharge’ is handled in a while on treatment strategy: see section 5.2.1
- Participants that discontinue the study before Day 28 will be considered as failure (Sustained clinical improvement at Day 28=no), unless they had an event of sustained clinical improvement prior to discontinuation. In the latter scenario it will be considered a success (Sustained clinical improvement at day 28=yes).

Population-level summary measure:

The difference in proportion of participants with of ‘Sustained clinical improvement at Day 28’ for experimental treatment versus placebo.

All-cause mortality up to Day 28

Population: The population of interest are hospitalized patients between ≥ 18 and <85 years old with confirmed critical COVID-19 disease.

Endpoint: Death by Day 28 (Yes/No)

Treatment: Sirukumab 5 mg/kg (IV single dose infusion on Day 1) and placebo (IV infusion on Day 1), both on top of SOC.

Intercurrent events:

- The intercurrent event of the use of prohibited medication is handled in a treatment policy strategy: data will be used as observed.
- Participants that discontinue the study before Day 28 with a score > 1 on the CRS will be analyzed according to the composite strategy and will be considered as death on day 28 (Death by day 28=yes).

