- Participants whose last score on the CRS was equal to 1 and that were not reported as having died before or at day 28 will be analyzed according to the composite strategy and they will be considered as alive (Death at Day 28=no).

Population level summary measure:

The difference in proportion of participants with ‘Death by day 28’ for experimental treatment versus placebo.

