5.4.2 Analysis Methods

The secondary endpoint evaluation will be conducted on the primary and on the ITT population.

Time-to event parameters

The time-to-event parameters will be evaluated based on the log-rank test, stratified for the stratification factors (age [<65 and ≥ 65 years] and use of IMV [yes/no]). The tests will be performed 1-sided at a 5% significance level. The actual values of the stratification factors will be used, not as randomized.

Cumulative proportion of patients with an event, by treatment, will be provided using the complement of the Kaplan Meier curve. The analyses will be completed with the median time to event (if reached) and the proportion of participants who with an event on day 7, 14, 21 and 28; all per Kaplan Meier method. The complementary log-log transform method is used to calculate the 90% confidence intervals.

Duration parameters

Descriptive statistics of the duration parameters will be shown for all participants that were still alive at day 28.

Total length of hospitalization and number of ventilation free days will be analyzed in the subgroup of participants that were still alive at day 28 by using the Hodges-Lehman approach. Corresponding 90% CIs will be presented as well.

Incidence parameters

For each parameter the number and percentage of participants in each category and subcategory will be tabulated and listed. All participants in the applicable analysis set will be counted for the denominator of the proportion.

The occurrence (yes/no) as described for the incidence parameters will be analyzed using logistic regression as described above (section 5.3).

Proportions: CRS outcome and CRS (As observed) outcome

A tabulation will be made of the CRS and CRS (As observed) outcomes at each day, taking only non-missing values into account (i.e.: the percentages of the six categories per day should sum up to 100%).

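### The logistic sensitivity analysis in SAP 5.3.3 evaluates the model at average covariates, so it estimates a different quantity from the difference in proportions named in the estimands

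*SAP*

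**What the plan says.** SAP 5.3.2 gives both key secondary estimands the same kind of summary measure. For improvement it begins "The difference in proportion of participants with of" and for death by Day 28 "The difference in proportion of participants with"; each compares sirukumab with placebo.

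SAP 5.3.3 takes as the main analysis "the CMH analysis for difference in proportions, adjusted for the stratification factors" (age and IMV), reported as a Mantel-Haenszel common risk difference. It then adds: "As a sensitivity analysis, a logistic regression model will be estimated that is adjusted for the treatment group, but also adjusted for additional baseline covariates". Covariates are chosen stepwise: "A covariate will be added to the model if it is significant at the 25% significance level". The threshold to stay is printed as 0.15%. Then: "In the final logistic regression model the treatment difference in proportions will be estimated". The per-arm proportion is "estimated using the average value observed the study (across treatment groups) for both the continues and categorical covariates", with 0/1 coding for categorical covariates and a delta-method interval. Averaging of individual predictions is not mentioned.

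SAP 5.4.2 says that occurrence of each other-secondary incidence endpoint "will be analyzed using logistic regression as described above", pointing back to section 5.3.

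**The concern.** The inverse logit is not linear, so the probability at the average covariate profile is not the average of the participants' probabilities. The SAP's calculation describes a person of fractional sex and race with mean IL-6, CRP and ferritin, yet it is labelled as a proportion of participants.

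A sensitivity analysis should differ from the main analysis only because its assumptions differ. Here the two can be several points apart even if the logistic model is exactly right and adjustment changes nothing. A reader could take an artefact of the formula for an effect of adjustment, or for added support.

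**Working it through.** **Inputs.** From SAP 1.4: 74 sirukumab and 37 control; improvement 30% vs 55%; key secondary mortality 40% vs 15%; one-sided 5%; at least 80% power for both. The prognostic strength of the covariates is not in the documents. It is assumed here and shown over a range.

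**The plan's own figure.** Power = Φ{[|p₁−p₂| − 1.645·√(p̄(1−p̄)(1/37+1/74))] / √(p₁(1−p₁)/37 + p₂(1−p₂)/74)}.
- Improvement: p̄ = (37×0.30 + 74×0.55)/111 = 0.467. Power = Φ[(0.25 − 1.645×0.1004)/0.0950] = 81%.
- Mortality: p̄ = (37×0.40 + 74×0.15)/111 = 0.233. Power = Φ[(0.25 − 1.645×0.0852)/0.0906] = 89%.

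The stated 80% is reproduced. The SAP gives no figure for the logistic difference itself.

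**A hand check.** Take one binary covariate with prevalence 50% and odds ratio 3.5, and choose intercepts so that the true proportions are 30% and 55%.
- Control probabilities are 0.175 and 0.425, with mean 0.300.
- Sirukumab probabilities are 0.400 and 0.700, with mean 0.550.
- The average of individual predictions therefore differs by 25 points.
- The SAP formula sets the covariate to 0.5, which averages the log-odds. Control odds are √(0.212×0.740) = 0.396, so p = 0.284. Sirukumab odds are √(0.667×2.333) = 1.247, so p = 0.555. The difference is 27.1 points.

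Two and three such covariates give 28.9 and 30.4 points. For mortality (40% vs 15%), one, two and three give 25.7, 26.3 and 26.7 points instead of 25.

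**General check.** Let the covariates contribute a normal score with SD s on the logit scale. For each arm solve a from E[expit(a + sZ)] = true rate; the SAP formula returns expit(a).

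| True rates | True difference (points) | s = 0.5 | s = 1 |
|---|---|---|---|
| 30% vs 55% | 25 | 26.3 | 29.5 |
| 40% vs 15% | 25 | 25.5 | 26.6 |
| 20% vs 10% | 10 | 9.7 | 9.0 |
| 10% vs 5% | 5 | 4.7 | 3.8 |
| 85% vs 95% | 10 | 9.5 | 8.1 |

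At s = 0 there is no gap. Standardisation returns the true difference in every cell.

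The sign change follows from the curvature of the logit. For a small effect and small s, marginal difference / plug-in difference ≈ 1 + (s²/2)(1 − 6p + 6p²). The bracket is negative, so the plug-in is larger, only for p between about 0.21 and 0.79.

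**With the SAP's selection rule.** 250 simulated trials per scenario, 74 vs 37, six covariates, s = 1. All values are mean differences in points; mortality is shown as a reduction.

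| Endpoint | Model | SAP formula | Standardised | No covariate retained |
|---|---|---|---|---|
| Improvement | all covariates | 29.7 | 24.2 | – |
| Improvement | stay 0.15% (as printed) | 26.5 | 24.2 | 48% of trials |
| Improvement | stay 15% | 29.3 | 24.2 | 0.4% |
| Mortality | all covariates | 28.6 | 26.2 | – |
| Mortality | stay 0.15% (as printed) | 26.5 | 25.7 | 62% of trials |

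The Mantel-Haenszel means in the same trials were 24.2 and 25.7, so the standardised estimate tracks the main analysis. Simulation error on a mean is about 9.5/√250 = 0.6 points.

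**The case against.** Four points count against giving this much weight.

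1. **No key secondary decision rests on it.** SAP 5.3.3 bases the treatment comparison on the CMH interval and p-value. The plug-in step leaves the fitted model, its treatment coefficient and that coefficient's p-value unchanged. This stands.
2. **The gap is often small or absent.** Under the printed stay rule, about half or more of the simulated trials retained no covariate. The mean gap was then 2.3 points for improvement (26.5 − 24.2) and 0.8 for mortality (26.5 − 25.7). The standard errors of the risk difference are about 9.5 and 9.1 points. This also stands, with two limits. The strict rule is easier to pass in the larger ITT set, where the key secondary analyses are repeated and baseline CRS (≤3 vs >3) actually varies. And the gap is a systematic shift, so more data do not remove it.
3. **The formula is openly stated.** A reader can see that it is a prediction at the means, so a new label would settle part of the problem. It would not make the result comparable with the Mantel-Haenszel difference.
4. **It does not always favour sirukumab.** A reader might infer that the formula inflates the benefit in general. The documents do not support that, because the direction depends on the event rate. If observed mortality were low, the formula would show a smaller benefit. For the SAP 5.4.2 incidence endpoints no rates are given, so no direction can be claimed.

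**Conclusion.** The mismatch is real and does not depend on any assumption. SAP 5.3.2 names a difference in the proportion of participants, and the step in SAP 5.3.3 computes something else whenever a prognostic covariate is retained.

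Its size does depend on assumptions. For s of 0.5 to 1 the excess at the planning rates is about 1 to 5 points for improvement and 0.5 to 1.6 for mortality. It turns into an understatement at low or high rates. A figure such as 33.7 points for improvement can be produced, but only at s = 1.5. One OR-3.5 covariate at 50% prevalence contributes an SD of ln(3.5)/2 = 0.63, so s = 1.5 needs about (1.5/0.63)² ≈ 6 of them, all retained with 111 participants. That is not a fair headline.

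Mortality has to be judged at 40% vs 15%, the key secondary target in SAP 1.4. The 40% vs 20% assumption there belongs to the primary endpoint's sample size.

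The CMH tests are untouched. The point matters more in SAP 5.4.2, where the logistic method, by reference to section 5.3, is the planned analysis and no CMH result is planned beside it. Protocol 9.4.4 instead sends several of these proportions to the key secondary technique, which Protocol 9.4.3.1 gives as CMH. The change is worth making before database lock, as an improvement to supportive analyses.

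**What to change.** Replace the plug-in sentence in SAP 5.3.3 with standardisation. From the final logistic model, predict every participant's probability with treatment set to sirukumab and again with treatment set to placebo. Average each set of predictions over all participants in the analysis set (Primary, and ITT for the repeat), and report the difference with a delta-method or bootstrap interval. In SAP 5.4.2, state that the incidence endpoints use the same standardised difference.

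The cost is a few lines of SAS and a small change of wording. No new data are needed, and the model and the covariate selection can stay as they are.
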